3.3 Assessment of approach to informing relatives of non-survivors

Our approach to informing the relatives of non-survivors has not previously been tested in the UK. We will review how this is received throughout the study by monitoring the number and nature of enquiries received by the Ambulance Service. We will monitor the time taken to identify next of kin, the sources consulted to verify next of kin details and the concordance/discordance between different sources.

3.4 Qualitative assessments – Nested studies

In order to support the quantitative findings from this feasibility study an exploratory sub-study of the experiences of those recruiting patients will be conducted. This will provide qualitative data allowing an understanding of the impact of the study on ambulance staff, enabling decisions regarding a large-scale trial to be taken that maximise its acceptability and effectiveness.[42] A

phenomenological approach will be taken towards understanding the experience of following the study processes and recruiting patients. Since management of cardiac arrest is a team endeavour, we will seek to understand not only the individuals' experience but also the culture within which they operate. We will use focus groups to elicit views and opinions and observe reactions to what is being said.

3.4.1 Aims and objectives

Aim:

To explore and describe the experience of paramedics delivering this study, specifically the barriers and facilitators to patient recruitment.

Objectives:

- To explore strategies for optimising treatment adherence
- To describe problems and possible solutions for improving the ease and reliability of data recording.

3.4.2 Sample

Maximum variation sampling will be employed to elicit a broad range of views from the ambulance staff.[41] We will invite staff, to include those who have and have not treated patients, from geographically disparate teams comprising a variety of clinical grades and length of experience to take part in the focus groups. We will complete 3-4 focus groups, which should allow us to reach data saturation.[43]

3.4.3 Recruitment and consent

Ambulance staff will be offered the opportunity to take part in focus groups mid-way through recruitment which will allow time for the study to bed down.[42]. Those expressing an interest to take part will be sent a Participant Information Sheet. On the day, the focus group facilitator will provide a verbal summary of the PIS before seeking consent. Participants will be asked for their consent to take part in the focus group, audio recording of data, transcription of data, re-contact by a research paramedic should clarification be required and publication of anonymised quotes. It will be made clear that it will not be possible to withdraw consent and have data removed once the focus groups have commenced.

3.4.4 Intervention

Focus groups will be conducted immediately following a team training session, conducted either at the normal Ambulance service premises or via an online platform if the meeting is to happen

remotely. This is the only time when groups are normally together at the same time. This will also provide the context within which people are used to having the practice-related discussions that shape their attitudes and behaviours.[44]

Pre-prepared topic guides will be used to initiate conversation if required. Groups will be audio recorded and transcribed by the researcher.

3.4.5 Data management and analysis

Electronic audio data files will be transcribed by the researcher.

Transcribed and text will be coded supported by NVivo data analysis software.[45] Analysis of the data will be conducted according to the six phases of thematic analysis.[46] Anonymised transcriptions will be stored on secure servers, that are backed up daily, for 10 years at WCTU.

4. ADVERSE EVENT MANAGEMENT

4.1 Definitions

4.1.1 Adverse Events (AE)

An Adverse Event (AE) is defined as any untoward medical occurrence in a participant taking part in healthcare research and which does not necessarily have a causal relationship with this treatment/intervention. A study CRF for the capture of AEs will be developed and reviewed by the CI, statistician and QA team. AEs will be reviewed and monitored by SOC for trends.

AEs occurring from the time of delivery of study treatment until hospital discharge 30 days post treatment (whichever is sooner) should be reported to WCTU via the appropriate CRF.

4.1.2 Serious Adverse Events (SAEs)

A Serious Adverse Event is an AE that fulfils one or more of the following criteria:

- Results in death
- Is immediately life-threatening
- Requires hospitalisation or prolongation of existing hospitalisation
- Results in persistent or significant disability or incapacity
- Is a congenital abnormality or birth defect
- Requires medical intervention to prevent one of the above, or is otherwise considered medically significant by the investigator (e.g. participant safety is jeopardised).

Many of the above-listed SAEs are associated with cardiac arrest and would be expected consequences of cardiac arrest and attempted resuscitation. Only unexpected, related events are reportable.

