Due to the life-threatening nature of the condition, cardiac arrest needs to be treated as quickly as possible. Without treatment the patient will not survive and a patient's chances of survival reduce by 7-10% with each minute of delay to resuscitation.[22] The study design ensures that there will be no interruption to delivery of defibrillation, CPR or other elements of resuscitation, which will be delivered in accordance with current UK Resuscitation Council guidelines.[23]

The Study Oversight Committee will monitor safety by tracking trends in survival.

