4.2 Reporting SAEs

Adverse and serious adverse events which are expected in this population of patients will not be reported, if thought to be unrelated to the trial interventions. These should not be reported as SAE.

Such conditions include:

- Death
- Is immediately life-threatening
- Hospitalisation
- Persistent or significant disability or incapacity
- Organ failure
- Injuries or complications associated with cardiac arrest or attempted resuscitation

All reportable **SAEs (as defined in section 4.1)** occurring from the time of delivery of study treatment until hospital discharge or 30 days post treatment (whichever is sooner) must be recorded on the SAE Form and sent to the Sponsor **within 24 hours** of the research staff becoming aware of the event. All SAEs must be reported to WCTU within 24 hours of becoming aware of an adverse event that fulfils the criteria for 'seriousness'. Notification may be received via email or telephone. Where full information is not immediately available, verbal reports will be documented and followed up with a written report as soon as possible. On receipt of notification, all SAEs will be reported immediately to the WCTU Quality Assurance (QA) team. A study CRF for the capture and

reporting of SAEs will be developed and reviewed by the CI, statistician and QA team. On receipt of the initial report the QA team will immediately log on the SAE database.

For each **SAE** the following information will be collected:

- full details in medical terms and case description
- event duration (start and end dates, if applicable)
- action taken
- outcome
- seriousness criteria
- causality (i.e. relatedness to intervention), in the opinion of the investigator
- whether the event would be considered expected or unexpected.

Any change of condition or other follow-up information should be uploaded to the study database as soon as it is available. Events will be followed up until the event has resolved or a final outcome has been reached.

The study coordinator will liaise with the investigator to compile all the necessary information. The study coordinating centre is responsible for reporting any related and unexpected SAEs to the sponsor and REC within required timelines.

The causality of SAEs (i.e. relationship to study treatment) will be assessed by the investigator(s) on the SAE form.

Relationship to study treatment	Description
Unrelated	There is no evidence of any causal relationship

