Unlikely to be related	There is little evidence to suggest there is a causal relationship (e.g. the event did not occur within a reasonable time after administration of the study intervention or device). There is another reasonable explanation for the event (e.g. the patient's clinical condition, other concomitant treatment).
Possible relationship	There is some evidence to suggest a causal relationship (e.g. because the event occurs within a reasonable time

	after administration of the study intervention or device). However, the influence of other factors may have contributed to the event (e.g. the patient's clinical condition, other concomitant treatments).
Probable relationship	There is evidence to suggest a causal relationship and the influence of other factors is unlikely.
Definitely related	There is clear evidence to suggest a causal relationship and other possible contributing factors can be ruled out.

The site PI will be responsible for ensuring that SAEs are reported within 24 hours of a member of the research team becoming aware of the event. Events shall be recordable until hospital discharge.

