4.3 Responsibilities

The SMG will monitor adverse events on a monthly basis. Cumulative review of all safety information will be conducted by the Study Oversight Committee on a 6-monthly basis. The CI will ensure that independent review of each SAE is conducted.

Principal Investigator (PI):

1. Using medical judgement in assigning seriousness, causality and expectedness
2. Ensuring that all SAEs are recorded and reported to the Sponsor within 24 hours of becoming aware of the event and provide further follow-up information as soon as available. Ensuring that SAEs are chased with Sponsor if a record of receipt is not received within 2 working days of initial reporting.
3. Ensuring that AEs are recorded and reported to the Sponsor in line with the requirements of the protocol.

Chief Investigator (CI) / Co-chief investigator:

1. Clinical oversight of the safety of patients participating in the study, including an ongoing review of the risk / benefit.
2. Using medical judgement in assigning seriousness, causality and expectedness of SAEs where it has not been possible to obtain local medical assessment.
3. Immediate review of all related and unexpected SAEs
4. Review of specific SAEs in accordance with the study risk assessment and protocol as detailed in the Study Monitoring Plan.
5. Production and submission of annual reports to the relevant REC.

Sponsor:

1. Central data collection and verification of AEs, and SAEs, according to the study protocol.
2. Reporting safety information to the CI, delegate or independent clinical reviewer for the ongoing assessment of the risk / benefit according to the Study Monitoring Plan.
3. Reporting safety information to the Study Oversight Committee (SOC) identified for the study according to the Study Monitoring Plan.
4. Expedited reporting of related and unexpected SAEs to the REC within required timelines.
5. Notifying Investigators of related and unexpected SAEs that occur within the study.

Study Oversight Committee (SOC):

In accordance with the Study Terms of Reference for the SOC, periodically reviewing safety data to determine patterns and trends of events, or to identify safety issues, which would not be apparent on an individual case basis.

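### Section 4 contradicts itself on which serious adverse events are reportable: an expected but related event is excluded by one sentence and included by another, and the reporting windows also differ

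*Protocol*

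**What the plan says.** All the statements are in Section 4 of the protocol.

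- **Section 4.1.2**, after listing the seriousness criteria and noting that many such events are expected after cardiac arrest: "Only unexpected, related events are reportable".
- **Section 4.2, opening** (where relatedness means relation to the interventions under study): "Adverse and serious adverse events which are expected in this population of patients will not be reported, if thought to be unrelated". It adds: "These should not be reported as SAE". The list of expected conditions includes death, hospitalisation, disability, organ failure, and injuries or complications of the arrest or the resuscitation attempt.
- **Section 4.2, next paragraph:** reportable SAEs, with a cross-reference to Section 4.1, go to the Sponsor within 24 hours. Then (the criteria being those of seriousness): "All SAEs must be reported to WCTU within 24 hours of becoming aware of an adverse event that fulfils the criteria".
- **Section 4.3, duties of the PI:** "Ensuring that all SAEs are recorded and reported to the Sponsor within 24 hours of becoming aware of the event".
- **Sections 4.2 and 4.3, onward reporting:** SAEs that are both related and unexpected go on to the REC.

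On the window, Section 4.2 ends SAE reporting at the earlier of hospital discharge and 30 days after treatment. Section 4.1.1 gives the same window for AEs, with the word 'or' missing. Section 4.2 then closes with "Events shall be recordable until hospital discharge", which has no 30-day limit.

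**The concern.** Someone deciding whether to complete an SAE form for a serious event that is expected after cardiac arrest, but is judged related to the shocks, gets opposite answers from Sections 4.1.2 and 4.2. This kind of event matters here. Section 1.2 says that too much energy may injure the myocardium, and the expected list in Section 4.2 is broad enough to take in many injuries and complications of resuscitation.

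If Section 4.1.2 is followed, such events get no SAE form, no causality assessment on that form, and none of the independent review that Section 4.3 promises for each SAE. Patients are enrolled under deferred consent (Section 2.7) and there is no DMC (Section 7.10). The Study Oversight Committee is the body expected to see patterns that single cases do not show (Section 4.3).

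**Working it through.** No sample size or error rate is involved, so the check is logical. Class each SAE as expected or unexpected and as related or unrelated, then apply each sentence to the four cells.

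| SAE is | 4.1.2, last sentence | 4.2, opening waiver | 4.2 and 4.3, 'all SAEs', read literally |
|---|---|---|---|
| Unexpected, related | report | report | report |
| Unexpected, unrelated | not reported | report | report |
| Expected, related | not reported | report | report |
| Expected, unrelated | not reported | not reported | report |
| Cells reported | 1 of 4 | 3 of 4 | 4 of 4 |

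**Does the waiver really conflict with 4.1.2?** It does so by implication. The waiver carries the condition that the event be thought unrelated. If every expected event were already excluded, that condition would do nothing.

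**Can the third column be reconciled with the others?** Yes, in two ways.

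1. The waiver removes its events first, and 'all SAEs' means those that remain. The third column then equals the second (3 of 4).
2. 'All SAEs' is short for the reportable SAEs of the preceding sentence, which points back to 4.1. The third column then equals the first (1 of 4).

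Under either reading the first two columns still disagree, in the same two rows.

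**Which reading fits the rest of Section 4?** Section 4.2 asks for causality and for expectedness on each SAE, and its causality scale includes unrelated and unlikely-related categories. The route to the REC is a further step restricted to related and unexpected SAEs. All of this presupposes that a wider set reaches the coordinating centre, so the layout fits the waiver and not the last sentence of 4.1.2.

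**A gap within the waiver.** The causality scale has five levels, but the waiver speaks only of events thought unrelated. It does not say whether an expected event rated unlikely to be related is waived.

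**Windows.** Let D be the day of discharge.

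- D at or before day 30: both windows close on day D, so there is no conflict.
- D after day 30: one closes on day 30 and the other on day D, a difference of D − 30 days.

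Table 2 marks adverse event reporting at the arrest and in hospital but not at day 30. It contradicts neither window.

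**The case against.** The strongest reply is that little would be lost in practice. Section 4.4 sends deaths to the SMG monthly and to the oversight committee every six months, whichever SAE rule is followed. Table 1 collects resulting rhythm after each shock, refibrillation and survival for participants. Section 4.1.1 sends AEs to WCTU for trend review. Most of this stands, and it narrows the exposure. It does not close it: these data carry no SAE causality judgement, other related injuries are not among the listed outcomes, and the AE route has no 24-hour limit.

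On the window, Section 4.2's closing line says 'recordable', so separate recording and reporting periods could be argued. The protocol draws no such distinction.

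Three stronger readings are tempting but not supported.

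- **Three incompatible rules.** A reader might infer this from the 1, 3 and 4 cells. The 'all SAEs' wording can be reconciled with either of the other two statements, so the firm conflict is between 4.1.2 and the waiver in 4.2.
- **A swing from almost no SAE reports to more than 70.** Applying the 20.9% survival in Section 1.1 gives 90 × (1 − 0.209) = 71 deaths. But Section 4.2 names death among the events waived when unrelated, and the 20.9% is for initially shockable rhythms, while Section 2.1 also enrols later ones.
- **Counts that cannot be compared between arms.** There is one site, the PI assigns causality and expectedness (Section 4.3), and nothing links the sentence followed to the allocation. No formal comparison is planned (Section 6.2.1).

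**Conclusion.** The contradiction is real and should be corrected. It affects two of the four kinds of SAE, and the one that matters most is expected but related. That result holds on every reading of the 'all SAEs' sentences. It rests on taking the condition in Section 4.2's waiver as meaningful.

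The practical size is limited. Deaths, post-shock rhythm, refibrillation and survival are captured outside the SAE system, so what is exposed is mainly other related injuries or complications that Section 4.2 lists as expected. The protocol gives no rate for these, so no count can be attached. A reader might infer that asystole and refibrillation would go unseen. That does not follow: Section 4.2 does not name them as expected, and both are collected as outcomes.

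The window conflict is smaller, confined to patients in hospital beyond day 30, whose number is not stated. Neither conflict touches the feasibility outcomes.

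**What to change.** Reconcile Sections 4.1.2, 4.2 and 4.3 into one rule for reporting from site to WCTU and the Sponsor, consistent with the waiver already in Section 4.2.

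1. Waive only SAEs that are both expected and unrelated. Report related SAEs whether or not they are expected.
2. Delete the last sentence of Section 4.1.2 or amend it to match.
3. Change 'all SAEs' to 'all reportable SAEs' in Section 4.2 and in the PI duty in Section 4.3. Correcting only one place would leave the inconsistency.
4. State on which side of the waiver an event rated unlikely to be related falls.
5. Keep the existing expedited route to the REC for related and unexpected SAEs.
6. Give one reporting window in Section 4.1.1 (restoring the missing 'or' if that window is kept) and in both places in Section 4.2. If recording and reporting are meant to have different windows, say so.

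The cost is a wording amendment, a short notice to the site, and a few more SAE forms than under Section 4.1.2 as it stands.

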4.2 Reporting SAEs

Adverse and serious adverse events which are expected in this population of patients will not be reported, if thought to be unrelated to the trial interventions. These should not be reported as SAE.

Such conditions include:

- Death
- Is immediately life-threatening
- Hospitalisation
- Persistent or significant disability or incapacity
- Organ failure
- Injuries or complications associated with cardiac arrest or attempted resuscitation

All reportable **SAEs (as defined in section 4.1)** occurring from the time of delivery of study treatment until hospital discharge or 30 days post treatment (whichever is sooner) must be recorded on the SAE Form and sent to the Sponsor **within 24 hours** of the research staff becoming aware of the event. All SAEs must be reported to WCTU within 24 hours of becoming aware of an adverse event that fulfils the criteria for 'seriousness'. Notification may be received via email or telephone. Where full information is not immediately available, verbal reports will be documented and followed up with a written report as soon as possible. On receipt of notification, all SAEs will be reported immediately to the WCTU Quality Assurance (QA) team. A study CRF for the capture and

reporting of SAEs will be developed and reviewed by the CI, statistician and QA team. On receipt of the initial report the QA team will immediately log on the SAE database.

For each **SAE** the following information will be collected:

- full details in medical terms and case description
- event duration (start and end dates, if applicable)
- action taken
- outcome
- seriousness criteria
- causality (i.e. relatedness to intervention), in the opinion of the investigator
- whether the event would be considered expected or unexpected.

Any change of condition or other follow-up information should be uploaded to the study database as soon as it is available. Events will be followed up until the event has resolved or a final outcome has been reached.

The study coordinator will liaise with the investigator to compile all the necessary information. The study coordinating centre is responsible for reporting any related and unexpected SAEs to the sponsor and REC within required timelines.

The causality of SAEs (i.e. relationship to study treatment) will be assessed by the investigator(s) on the SAE form.

Relationship to study treatment	Description
Unrelated	There is no evidence of any causal relationship
Unlikely to be related	There is little evidence to suggest there is a causal relationship (e.g. the event did not occur within a reasonable time after administration of the study intervention or device). There is another reasonable explanation for the event (e.g. the patient's clinical condition, other concomitant treatment).
Possible relationship	There is some evidence to suggest a causal relationship (e.g. because the event occurs within a reasonable time

	after administration of the study intervention or device). However, the influence of other factors may have contributed to the event (e.g. the patient's clinical condition, other concomitant treatments).
Probable relationship	There is evidence to suggest a causal relationship and the influence of other factors is unlikely.
Definitely related	There is clear evidence to suggest a causal relationship and other possible contributing factors can be ruled out.

The site PI will be responsible for ensuring that SAEs are reported within 24 hours of a member of the research team becoming aware of the event. Events shall be recordable until hospital discharge.

4.3 Responsibilities

The SMG will monitor adverse events on a monthly basis. Cumulative review of all safety information will be conducted by the Study Oversight Committee on a 6-monthly basis. The CI will ensure that independent review of each SAE is conducted.

Principal Investigator (PI):

1. Using medical judgement in assigning seriousness, causality and expectedness
2. Ensuring that all SAEs are recorded and reported to the Sponsor within 24 hours of becoming aware of the event and provide further follow-up information as soon as available. Ensuring that SAEs are chased with Sponsor if a record of receipt is not received within 2 working days of initial reporting.
3. Ensuring that AEs are recorded and reported to the Sponsor in line with the requirements of the protocol.

Chief Investigator (CI) / Co-chief investigator:

1. Clinical oversight of the safety of patients participating in the study, including an ongoing review of the risk / benefit.
2. Using medical judgement in assigning seriousness, causality and expectedness of SAEs where it has not been possible to obtain local medical assessment.
3. Immediate review of all related and unexpected SAEs
4. Review of specific SAEs in accordance with the study risk assessment and protocol as detailed in the Study Monitoring Plan.
5. Production and submission of annual reports to the relevant REC.

Sponsor:

1. Central data collection and verification of AEs, and SAEs, according to the study protocol.
2. Reporting safety information to the CI, delegate or independent clinical reviewer for the ongoing assessment of the risk / benefit according to the Study Monitoring Plan.
3. Reporting safety information to the Study Oversight Committee (SOC) identified for the study according to the Study Monitoring Plan.
4. Expedited reporting of related and unexpected SAEs to the REC within required timelines.
5. Notifying Investigators of related and unexpected SAEs that occur within the study.

Study Oversight Committee (SOC):

In accordance with the Study Terms of Reference for the SOC, periodically reviewing safety data to determine patterns and trends of events, or to identify safety issues, which would not be apparent on an individual case basis.

